The primary goal of the trial intervention will be a test of the feasibility of Coaching-CRAFT, CSO’s experience and engagement in the intervention, and within-subject estimates of changes in Veterans’ engagement in treatment. We will seek to enter 50 family member callers into a nonrandomized trial over 6 months. Each research-based telephone contact will be audio recorded for examination using the fidelity scale developed in months 1-4.

An additional goal is to compare the outcome in the trial to a usual-care sample of at least 50 CIC callers that have not been offered Coaching-CRAFT, matched on the basis of the Veteran’s primary substance use problem(s), relationship of CSO to Veteran, contact time and co-habiting

status, Veteran age and gender, and race. We will select comparison cases from a several year time-frame to ensure an appropriate comparison.

The length of the active coaching of the CSO using the web-based CRAFT material is anticipated to last no longer than 6 months, but this will be determined by the treatment manual development phase. Additional assessments will occur at 6 and 12 months after study entry and will include the measures as detailed in the table (above). *At 12 months, we will ask the CSO to invite the Veteran to engage in the study and answer study questions about their symptoms, treatment, and the CSO's approach to them.* We will carefully assess the safety and risk to the CSO-Veteran relationship prior to making the decision to pursue this assessment. Working with the CSO, we will ask the CSO to ask the Veteran to be involved, including type of discussion between CSO and Veteran might be helpful, and ask the CSO to ask the Veteran to call the study staff (see Human Subjects).

Timeline

We anticipate the trial will begin in Year 1 with initial recruitment occurring from months 5-10. The trial will end in Year 2, month 22. Analyses of feasibility, satisfaction and treatment engagement will occur in months 19-24. After the formal participation in the trial, any caller who needs additional support or treatment referral will be referred to the CIC call center.

Data Analysis, Sample Size considerations, and intervention modification

Feasibility Outcomes

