We will examine CSOs ratings of the intervention with a criterion of at least 80% of those rating the intervention as helpful, leading to increased hopefulness and preparedness to help the Veteran, and that the intervention had helped the family overall. We will also examine the degree to which the subjective symptoms of distress (PHQ-9, subjective burden), decline over the Baseline, 6 month, and 12 month assessments, using a mixed methods model test of within-subjects change over time. We will compare the completion rates of the Coaching-CRAFT sample of CSOs with a sample of CSOs from the CIC QA data. "Completion" will mean at least 6 months of telephone coaching of 8+ calls. We will match CSOs receiving Coaching-CRAFT with the treatment as usual data (see above).

Intervention comparisons

In a key analysis we will also plan to test the proportion of the Veterans of the CSOs who entered treatment for substance misuse against the matched CSOs from the CIC QA data. We will use an intent-to-treat approach. Those CSOs lost to follow-up will be deemed intervention failures regarding the Veterans' engagement in treatment. We plan to use a basic test of difference between proportions in independent samples (a two sample z-test). To detect a difference between the rate of engagement in treatment using CIC QA data (i.e., 41%) and conservative outcomes drawn from the CRAFT RCTs (67%), the sample group needed to detect a difference with power of 80% in post-intervention treatment engagement outcomes, is $N = 45$, for each group [29]. Our intent-to-treat sample size of $N = 50$ exceeds this number.

Review of CSO and Veteran report: *Qualitative and treatment engagement reports*

We plan to conduct a systematic review of the responses to the post-intervention open-ended questions in order to modify the intervention as needed in preparation for a large RCT. In addition, we plan to assess the rate of Veteran inclusion in the study at 12 months, *the CSO report, the VHA report of Veteran treatment utilization, and the comparison of these different data sources.*

Considerations of alternative approaches

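### The matched usual-care comparison is to be tested with an unadjusted independent-samples z-test, which ignores the matching and leaves any remaining imbalance on the matching variables uncorrected

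*Combined protocol and SAP*

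**What the plan says.** The Trial procedures section plans "a usual-care sample of at least 50 CIC callers that have not been offered Coaching-CRAFT". These callers are to be "matched on the basis of the Veteran’s primary substance use problem(s), relationship of CSO to Veteran, contact time and co-habiting" and on further Veteran characteristics. In all there are seven variables: primary substance problem, relationship, contact time, co-habitation, Veteran age, Veteran gender and race. On timing, the same section says "We will select comparison cases from a several year time-frame".

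Under Intervention comparisons, in the data analysis section, the proportion of Veterans entering substance-misuse treatment is tested "against the matched CSOs from the CIC QA data". The plan describes this analysis as key, and the named method is "a basic test of difference between proportions in independent samples (a two sample z-test". The sample size (45 per group, with 50 planned) is also an independent-samples calculation, for 41% against 67%.

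The plan does not state a matching ratio or algorithm, and it does not say whether matching is caller by caller or by group frequency. It specifies no matched, stratified or covariate-adjusted analysis, no balance check and no sensitivity analysis for this comparison.

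**The concern.** The design and the analysis do not fit together. Matching is worth doing when the matching variables are related to the outcome. In that case the outcomes of matched callers are positively correlated, and a test that treats the groups as unrelated overstates the variance of the difference. Some of the precision gained by matching is lost.

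The second issue is bias. Matching on seven variables, at least two of them (age and contact time) not naturally categorical, is unlikely to be exact. A plain z-test carries any remaining difference straight into the estimated effect. The comparison is not randomised, so chance balance cannot be relied on. The variables needed to correct it must already be in hand, because the matching uses them.

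**Working it through.** **Inputs.** The rates 41% and 67%, 80% power and 50 per group come from Intervention comparisons. Alpha and sidedness are not stated; 0.05 is assumed. The within-pair correlation ρ is not given; values from 0 to 0.2 are assumed. The calculations under the second and third steps assume 1:1 pairs, which the plan does not state.

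**The plan's own figure.** With pooled variance under the null:

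n = [z_α·√(2·0.54·0.46) + 0.842·√(0.2211 + 0.2419)]² / 0.26²

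- One-sided 0.05: (1.645·0.7048 + 0.842·0.6804)² / 0.0676 = 44.4, so 45. This reproduces the stated figure.
- Two-sided 0.05: (1.960·0.7048 + 0.842·0.6804)² / 0.0676 = 56.5, so 57.

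At 50 per group the z-test has about 84% power one-sided and 75% two-sided, treating the groups as independent.

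**Standard error under pairing.** With p₁ = 0.67 and p₂ = 0.41:

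Var(difference) = [p₁q₁ + p₂q₂ − 2ρ√(p₁q₁p₂q₂)] / 50 = [0.4630 − 2ρ·0.2313] / 50

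The independent-samples SE is the value at ρ = 0.

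**Real size of the nominal 5% two-sided z-test.** Under the null with a common rate, the true variance is (1 − ρ) times the planned one. The size is therefore 2[1 − Φ(1.96/√(1 − ρ))].

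| ρ (assumed) | Correct SE | Planned SE (0.0962) too wide by | Real size |
|---|---|---|---|
| 0 | 0.0962 | 0% | 5.0% |
| 0.05 | 0.0938 | 2.6% | 4.4% |
| 0.1 | 0.0913 | 5.4% | 3.9% |
| 0.2 | 0.0861 | 12% | 2.8% |

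By normal approximation at two-sided 0.05, power for the z-test and for a McNemar test is 75% and 73% at ρ = 0, 76% and 77% at 0.1, and 77% and 81% at 0.2.

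**Remaining imbalance.** Suppose there is no true effect, but imbalance adds a spurious difference b to the 41% rate. The probability of rejection is 1 − Φ((1.96·SE₀ − b)/SE₁) + Φ((−1.96·SE₀ − b)/SE₁), where SE₀ is the pooled and SE₁ the unpooled standard error.

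- b = 0.05: SE₀ = 0.0992 and SE₁ = 0.0990, giving 7.9%.
- b = 0.10: SE₀ = 0.0997 and SE₁ = 0.0992, giving 17.0%.

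These values of b only illustrate sensitivity. Nothing in the documents estimates the imbalance that would remain.

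**Limits on an adjusted model.** At the planning rates the expected number of Veterans not entering treatment is 50·0.33 + 50·0.59 = 46. All seven matching variables, several with more than two categories, would need roughly 10 to 12 parameters, which is too many.

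Calendar time is a separate problem. Trial callers enter over six months, while comparators span several years. Assume comparators spread evenly over the three years before a six-month recruitment period:

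- The group means in time differ by 0.25 − (−1.5) = 1.75 years.
- Between-group variance is (1.75/2)² = 0.766. Average within-group variance is (0.5²/12 + 3²/12)/2 = 0.385.
- The squared correlation of group with time is 0.766/(0.766 + 0.385) = 0.665.
- The SE rises by 1/√(1 − 0.665) = 1.73, from 0.096 to about 0.17. Two-sided power is then about 35%.

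**The case against.** The strongest reply is that the standard-error problem may hardly exist. The plan never describes pairs, and a group of comparators matched on characteristics could equally mean frequency matching. Even with pairs, the correlation may be small: at 0.05 the planned SE is under 3% too wide, and at 0.02 about 1%. The error is conservative. If the one-sided 0.05 test that reproduces 45 is what the sponsor intends, the z-test at 50 per group already exceeds the 80% target. Inexact matching also weakens the correlation, so the two halves of the concern partly offset each other. Finally, Trial procedures ranks the comparison as an additional goal, and the closing section on alternative approaches puts feasibility ahead of efficacy. All of this stands, and it limits the importance of the point.

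It does not answer the bias half. Remaining imbalance on recorded variables is not conservative, and the plan neither checks nor adjusts for it.

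A reader might infer three stronger things that the documents do not support:

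- **That having "usual-care sample of at least 50 CIC callers that have not been offered Coaching-CRAFT" means pooling would undo the matching.** A fixed ratio above 1:1 keeps the balance when pooled. Only a variable ratio causes the problem, and none is planned.
- **That the pool is too small for good matches.** The recruitment section estimates about 600 callers a year who are close relatives of such Veterans with substance misuse, and comparators come from several years. The 109 callers in the preliminary data are one subsample and do not bound the pool.
- **That a McNemar test is the required analysis.** It needs 1:1 pairs, which the plan does not state.

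**Conclusion.** The mismatch is in the text: comparators matched on seven variables are analysed with an unadjusted independent-samples test. Its effect on the standard error ranges from nothing to about 12% over assumed correlations of 0 to 0.2 with 1:1 pairs, always towards caution when the correlation is positive. It would be wrong to read this half as false-positive inflation. The second effect, uncorrected imbalance on the matching variables, could bias the difference either way. The false-positive rates of 7.9% and 17.0% rest on assumed biases and are not estimates for this trial.

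The change is worth making because the analysis is described as key, carries the only sample-size calculation, and can be improved with data already held. It is not essential to the study: satisfaction ratings and within-subject changes do not depend on this test.

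Adjustment will not make the comparison free of confounding. Treatment status at the start, for example, is not on the matching list. Trial entry requires a Veteran not in treatment, while 35 of the 109 QA substance-misuse cases (32%) were already in care. Adjusting for the matching variables would not correct that.

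**What to change.** State the matching ratio and method, and report balance on all seven variables after matching. Then replace the z-test as the main analysis with a sparse adjusted comparison:

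- Fit a logistic model with group and a few matching variables named in advance, for example primary substance, relationship, co-habitation and Veteran age.
- Report a standardised risk difference with a confidence interval. Cluster standard errors on matched set if matching is by set; use robust standard errors if it is by frequency.
- Weight comparators within set only if the number per trial caller varies.
- Leave calendar year out of the main model, because it is nearly confounded with group.
- Keep the two-sample z-test as a supportive analysis.

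The cost is a short paragraph in the plan and slightly more programming, with no new data or participants. With about 100 subjects the number of covariates must stay small, so some matching variables will go unadjusted. Confounding by anything neither matched nor recorded will remain and should be stated as a limitation.

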[name] began CIC in 2010 as a pilot project and continues as the Director. Coaching Into Care has grown significantly since 2011 when it became a national program; in 2014 alone, CIC received over 3000 initial (incoming) calls. About 50% concerned a Veteran from the OEF/OIF/OND eras. About 70% of the calls in 2014 concerned psychosocial issues, including mental health, substance abuse, and/or behavioral concerns that may have an impact on the Veterans' or others' physical safety. Seventy-five percent of the callers were female, with 28% of them being a spouse or other intimate partner, 19% parents, 12% were sons, daughters or siblings, 28% were other types of family members, friends or other relationships. Thirteen percent of the calls were directly from Veterans about mental health, benefits, or other concerns. Virtually all of the callers to CIC have internet access; exceptions tend to be older callers and/or those with lower financial resources.

Quality Assurance (QA) data from our call center operations have indicated that the service is highly rated by callers but the impact of the service may be limited, especially in the cases of substance misuse. Within about 3 months of first calling, the treatment engagement of the Veteran who is the subject of the calls with CIC rises modestly [11]. In 939 CSO callers who started coaching since November 2014 whose concerns were specifically focused on mental health problems and no substance misuse of the Veteran, 248 of the Veterans were engaged in mental health care; this number rose 54% to 382 at follow-up. CSO callers had at least one call with a coach and some had more than 20. For a separate subsample of 109 callers of Veterans with substance misuse who entered coaching, the rate of treatment rose a more modest 40%, or 35 to 49 Veterans in care. In these uncontrolled findings the initial treatment engagement rate of those who entered coaching was somewhat higher for those with substance misuse vs. no substance misuse (34% vs 26%). It does appear, however, that additional systematic strategies are needed for those Veterans with substance misuse problems. See the Appendix for CIC Manuals.

Preliminary feasibility test of the web-based delivery of CRAFT for PTSD

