Recruitment for the sample in the trial will occur within the regular workflow of the CIC call center. We have estimated that on a yearly basis approximately 600 callers to CIC are first degree relatives of an OEF-OIF-OND Veteran who has a primary difficulty with substance misuse, yielding 300 potential referrals for the 6 active recruitment months of the trial. Initial assessment and problem identification has typically been conducted by a CIC call responder in the first 1-3 calls, often involving consultation with a licensed supervisor. Potential participants include the following: 1) CSO is a sibling, spouse/ intimate partner, or parent of a US military Veteran who served in Iraq or Afghanistan since 2001, 2) by the report of the CSO the Veteran of interest has a substance abuse problem that has led to interpersonal, legal, occupational, and/or health related negative consequences, 3) the CSO reports that the Veteran is not currently receiving treatment for this problem, and 4) the CSO has contact 4+times/week and lives with or within 30 min. of the Veteran. Exclusion criteria include: 1) CSO has an SUD (Form 90, see Measures), 2) the Veteran is currently incarcerated, 3) the CSO has no computer or other device with Internet access able to view video content, and 4) the CSO or Veteran likely has a psychotic disorder (CSO report on the MINI) (see Measures). Potential participants will be presented the option of being involved in the research trial, and if interested, will be contacted by the research staff. If the CSO is interested after hearing more details the research staff will conduct the additional screening, consent procedures, and baseline assessment. *We will also engage Veterans in the study at two points. First, if/when the CSO indicates that the Veteran wants treatment, we will offer help to the Veteran in an initial telephone conversation. In this conversation we will ask to use their responses as research data. Second, we will ask the CSO at 12 months after the baseline to invite the Veteran to participate (see below).*

Measures.

Demographic information (from CSO). Age, gender, race, marital status, relationship of CSO to the Veteran, living status (i.e., with the Veteran), hours in contact per week, Veteran's military service details (branch, highest rank, combat deployments, National Guard/Reserve component vs. regular Army/Navy/Marines/Air Force), Veteran's age, race, marital status, and number of children.

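### Key comparison: QA comparators are not required to be untreated at first call, the 41% control rate is not derived and is not a new-entry rate, and N = 45 holds only at an unstated one-sided 5% level

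*Combined protocol and SAP*

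**What the plan says.** **Trial entry.** Under Sample and recruitment procedures, a family member (CSO) is eligible only if "the CSO reports that the Veteran is not currently receiving treatment for this problem".

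**Comparators.** Trial procedures calls for "a usual-care sample of at least 50 CIC callers that have not been offered Coaching-CRAFT". The matching variables are the Veteran's "primary substance use problem(s), relationship of CSO to Veteran, contact time and co-habiting" status, plus Veteran age, gender and race. The Overview is no stricter: type of misuse and demographics. No section applies the trial's entry criteria to the QA cases.

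**Endpoint and test.** Intervention comparisons tests "the proportion of the Veterans of the CSOs who entered treatment for substance misuse against the matched CSOs from the CIC QA data" with a two-sample z-test, and counts CSOs lost to follow-up as failures. The sample-size sentence uses a different term: "power of 80% in post-intervention treatment engagement outcomes".

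**Sample size.** The rates are "the rate of engagement in treatment using CIC QA data (i.e., 41%) and conservative outcomes drawn from the CRAFT RCTs (67"%), giving 45 per group, with 50 planned. No alpha or number of sides appears anywhere.

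**QA data shown.** Under Preliminary Studies, for 109 callers about Veterans with substance misuse, "the rate of treatment rose a more modest 40%, or 35 to 49 Veterans in care". For 939 callers with no substance misuse, the number in mental health care went from 248 to 382. Follow-up was about 3 months from first call. In the trial, "Additional assessments will occur at 6 and 12 months after study entry".

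**The concern.** The two groups can differ on the variable closest to the outcome. Every trial Veteran starts untreated; a QA comparator drawn by the list as written need not. The plan does not say how a comparator already in treatment counts, and its two endpoint terms point to different answers. Depending on the choice, the usual-care rate can move up or down, and a larger sample would not remove the bias.

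The sample-size statement has a related weakness. Its control rate is given without numerator, denominator, subgroup or time point, and the QA rates shown measure something other than new entry. Because alpha and sidedness are missing, a reader cannot tell whether 50 per group meets the stated 80% power.

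Feasibility is the primary goal, but the plan calls this comparison key, gives it a power calculation, and describes the study as preparation for a large randomized trial. A biased contrast could mislead that decision either way.

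**Working it through.** **1. Reproduce N = 45.** Inputs (Intervention comparisons): p1 = 0.41, p2 = 0.67, power 80%, equal groups. With d = p2 − p1 = 0.26 and p̄ = 0.54, the pooled-variance z-test gives

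n = [z_α √(2p̄(1−p̄)) + z_β √(p1(1−p1) + p2(1−p2))]² / d²

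where √(2 × 0.54 × 0.46) = 0.7048, √(0.2419 + 0.2211) = 0.6804, z_β = 0.8416.

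- One-sided 5% (same as two-sided 10%), z_α = 1.645: (1.159 + 0.573)² / 0.0676 = 44.4, so **45**. Reproduced.
- Two-sided 5%, z_α = 1.960: (1.381 + 0.573)² / 0.0676 = 56.5, so **57**.

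The arcsine formula also gives 45 and 57; the unpooled formula gives 43 and 54. Power at 50 per group is Φ[(0.26√50 − z_α × 0.7048) / 0.6804]: **84%** one-sided, **75%** two-sided.

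**2. Look for the 41%** (Preliminary Studies).

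| QA group | In care at first call | In care at follow-up |
|---|---|---|
| Substance misuse | 35/109 = 32.1% | 49/109 = 45.0% |
| No substance misuse | 248/939 = 26.4% | 382/939 = 40.7% |
| Pooled | 283/1048 = 27.0% | 431/1048 = 41.1% |

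41% agrees by rounding with the second or third row, not the first. The 95% Wilson interval for 49/109 is 36% to 54%, so 41% is compatible with the substance-misuse rate without being that rate. With 45.0% against 67%, the requirement is 62 (one-sided 5%) or 79 (two-sided 5%) per group, and power at 50 is 72% or 61%.

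The text gives initial engagement in the substance-misuse group as 34%, but 35/109 is 32.1%. A rate of 34% needs 37 of 109, or a denominator near 103 (35/0.34 = 102.9). With 103, follow-up would be 49/103 = 47.6%. The count or the denominator is therefore uncertain.

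**3. How many comparators could be already treated.** 50 × 35/109 = 16.1, about 16 of 50. This is an upper figure, because the text does not say that the 35 were in care for substance misuse.

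**4. Effect on the usual-care rate.** Assume that the 109 stand in for the comparator pool and that being in care is the engagement endpoint. Let x be the number of the 35 who had left care by follow-up; the documents do not give x. New entries are then 49 − (35 − x) = 14 + x, among 109 − 35 = 74 untreated Veterans.

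| x (illustrative) | New entry, (14+x)/74 | In care at follow-up, 49/109 | Entry over all, (14+x)/109 |
|---|---|---|---|
| 0 | 18.9% | 45.0% (26 points too high) | 12.8% (6 too low) |
| 10 | 32.4% | 45.0% (13 too high) | 22.0% (10 too low) |
| 20 | 45.9% | 45.0% (1 too low) | 31.2% (15 too low) |

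- Third column, already-treated Veterans counted by status at follow-up: usual care is overstated whenever (14+x)/74 < 49/109, that is, for x up to 19.
- Fourth column, they stay in the denominator uncounted: the rate is 74/109 = 0.68 of the true entry rate whatever x is. With no true effect and 50 per group, a one-sided 5% test would favour Coaching-CRAFT 21% of the time at x = 0 and 32% at x = 10.

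**5. Power if comparators are restricted to untreated Veterans.** Against 67%, two-sided 5%, 50 per group: over 99% at x = 0, 94% at x = 10, 76% at x = 16, 57% at x = 20. It depends on a rate that has to come from the QA records.

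**The case against.** Four objections have force.

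- **Weight.** This is an additional goal in a nonrandomized pilot whose stated focus is proof of concept and feasibility rather than efficacy. True, and it limits how serious the point is. It does not excuse a comparison group that differs by design in an analysis the plan calls key.
- **The test sentence is clear enough.** A Veteran already in treatment cannot enter it, so counting such Veterans as engaged is the less natural reading. I agree. But the more natural reading leaves them in the denominator with no possibility of success, which biases the result towards Coaching-CRAFT.
- **In care is not the same as in treatment for substance misuse.** Some of the 35 may have been in other care and would have passed the trial's criterion. This stands, and is why 16 of 50 is an upper figure.
- **One-sided 5% is a permissible choice.** Also true. A reader might infer an arithmetic error in N = 45; there is none. The gap is that the choice is not stated.

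Two further inferences about the 41% go too far. It is not unsourced: the plan names the QA data, and what is missing is the derivation. Nor do the documents show that it was taken from callers with no substance misuse; the match is by rounding, and another extract is possible.

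**Conclusion.** The point holds in three parts.

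1. The matching list as written allows comparators who were already in treatment, up to about 16 of 50 on the only sample shown. The direction of the bias depends on a counting rule the plan does not give: downward for usual care on the more natural reading, and upward on the other unless more than 19 of the 35 had left care.
2. The 41% is attributed but not derived. It differs from the 45.0% shown for substance misuse, and all the QA rates shown are totals in care at about 3 months, not new entry among the untreated over the trial's 6 or 12 months.
3. N = 45 holds at one-sided 5%. At two-sided 5% it is 57, and 50 per group gives 75% power rather than 80%.

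The omission in part 1 and the arithmetic in part 3 do not depend on x; the sizes in points do, and are illustrations only. A reader might infer that the study must enrol more, or that 50 per group is certainly enough once comparators are restricted. Neither follows: restriction lowers the control rate below the total in care at the smaller values of x, which helps power, but a larger x or a longer window could raise it. The matter should be fixed before comparators are drawn; it does not undermine the feasibility aims.

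**What to change.** - **Trial procedures:** add that QA comparators are limited to callers whose Veteran was not in treatment for substance misuse at first call.
- **Intervention comparisons, endpoint:** define it as new entry into substance-misuse treatment, use that term in both the test and the power statement, and apply the same follow-up window in both groups. Comparing 3-month usual care with 6- or 12-month Coaching-CRAFT would favour the intervention even after the first change.
- **Control rate:** replace 41% with the new-entry rate in that QA subset, giving numerator, denominator and window. Reconcile the 34% with 35/109 at the same time. Do not write the illustrative values of x into the plan.
- **Alpha and sidedness:** state both, and restate power or the detectable rate at 50 per group. On the present inputs (41% against 67%) power is 84% at one-sided 5% and 75% at two-sided 5%; recompute once the QA rate is extracted.

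The cost is one selection rule, one query of existing QA records, and a reworded paragraph. The downside is a smaller comparator pool (74 of the 109 shown if all 35 are excluded, before other matching), eased by the several-year time-frame the plan already allows. If QA records do not reach 6 or 12 months, the common window has to be one that both sources cover.

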CRAFT has received a great deal of empirical support for the ability to increase treatment seeking and engagement in SUD treatment [12]. In 4 randomized clinical trials comparing CRAFT to a traditional approach (i.e., Al-Anon or Nar-Anon) in getting the person with alcohol or substance use problems to seek treatment, CRAFT demonstrated consistent superiority. The smallest between-group margin was 64% (CRAFT) vs. 30% (Control) [12, 13]. The largest margin reported was 86% vs. 0%, and most of the studies showed that CRAFT increases CSOs' mental and physical health. Despite

Acronyms/terms:

SUD = Substance Use Disorder

OEF-OIF-OND = Veterans of the Iraq and Afghanistan wars

CSO = Concerned Significant Other

CRAFT = Community Reinforcement and Family Training intervention

CIC = VA's Coaching Into Care call center

VA-CRAFT = Web-based online course for delivering CRAFT

Coaching-CRAFT = CIC coaching + VA-CRAFT online course

this empirical support, it is a face-to-face intervention that requires a great deal of time, resources, and access to trained providers, all of which may limit availability and successful outcomes.

Our approach is to combine the strengths of a telephone-based coaching strategy for CSOs with the structure of the CRAFT concepts in an intervention we call Coaching-CRAFT. Our research team for this proposal has developed a systematic web-based delivery of CRAFT (VA-CRAFT) in an educational course that focuses on the CSO helping the Veteran to engage in treatment (see Preliminary Studies, below). Our initial data show that this web-based material may not fully engage CSO's in changing their behavior toward the Veteran without some additional support, encouragement and guidance. Thus, neither the existing CIC coaching strategy nor the VA-CRAFT educational course alone appear sufficient to increase Veteran engagement in care for substance misuse; however, combining the telephone based service (i.e., Coaching Into Care) with the web course to help deliver CRAFT concepts is promising.

Preliminary Studies

Coaching Into Care (CIC) call center

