Co-Investigators [name] and [name] have recently led a group in the development of a web-based version of CRAFT (VA-CRAFT) for CSOs of Veterans. They are currently completing an HSR&D funded pilot randomized clinical trial of the VA-CRAFT among family members of Army National Guard Veterans who had returned from combat missions to Iraq and Afghanistan. Family members of Veterans who had screened positive for PTSD (some had comorbid SUD) but who were not engaged in mental health services were randomly assigned to complete the VA-CRAFT online training (n = 34) or a wait-list condition (n = 32). VA-CRAFT participants were reminded to log in every few weeks when needed but no coaching or support was provided. Preliminary analyses suggested that VA-CRAFT did not lead to greater engagement in VA mental health or SUD treatment in the three months following initiation of VA-CRAFT than the CSOs in the wait-list condition. However, there was a significantly greater decrease in CSOs reports of caregiver burden in the VA-CRAFT group (from 1.92 to 1.56) than the control group (from 1.81 to 1.84, interaction $p < .0001$). Qualitative interviews with 20 CSOs who

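### The 67% planning rate is called conservative but is underived and above the 64% CRAFT rate the protocol cites; N = 45 also needs an undeclared one-sided 5% test

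*Combined protocol and SAP*

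**What the plan says.** The section Intervention comparisons sets the control rate as "the rate of engagement in treatment using CIC QA data (i.e., 41"%) and takes the intervention rate from "conservative outcomes drawn from the CRAFT RCTs (67"%). On the analysis it says: "We plan to use a basic test of difference between proportions in independent samples (a two sample z-test"). It then gives "the sample group needed to detect a difference with power of 80"% as the target, and the answer "is $N = 45$, for each group [29"], and notes that the intent-to-treat sample of 50 is larger. Neither the significance level nor the number of sides is stated, and the source of 67% is not shown.

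Background and Significance quotes two CRAFT results from four randomized trials: "The smallest between-group margin was 64% (CRAFT) vs. 30% (Control") and "The largest margin reported was 86% vs. 0"%. The figure of 67% does not appear there.

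Two other places bear on the calculation. Trial procedures asks for a usual-care sample of 50 or more callers, chosen from several years of data. The call-center section of Preliminary Studies reports 49 of 109 Veterans in care at follow-up among substance-misuse callers, and 382 of 939 among callers with no substance misuse.

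**The concern.** A conservative planning rate should sit at or below the weaker end of the evidence it is drawn from. Here 67% is three points above the lower of the two CRAFT rates that the protocol quotes, and nothing explains the choice. At 50 per group a few points on the intervention rate decide whether the 80% target is met, so the label matters.

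The stated sample size also rests on a test convention that the reader has to guess. If the comparison is reported with the usual two-sided 5% test, the plan falls short of 80% power even at 67%. What is at stake is how a non-significant comparison is read: the protocol would have claimed adequate power for a test that did not have it, while using the pilot to prepare a larger trial.

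**Working it through.** **Inputs.** Control rate p1 = 0.41, planned rate p2 = 0.67, power 80% and n = 50 per group come from Intervention comparisons. The alternative p2 = 0.64 comes from Background and Significance. Alpha = 0.05 is my assumption; one-sided and two-sided are both shown.

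**Formulas** (pooled two-sample z-test, equal groups, no continuity correction), with p̄ = (p1 + p2)/2:

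- n = [z_α √(2p̄(1−p̄)) + z_β √(p1(1−p1) + p2(1−p2))]² / (p2 − p1)²
- power = Φ{[(p2 − p1) − z_α √(2p̄(1−p̄)/n)] / √([p1(1−p1) + p2(1−p2)]/n)}

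Here z_β = 0.842, and z_α = 1.645 (one-sided) or 1.960 (two-sided).

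**Step 1: reproduce the stated 45.** For 41% v 67%, p̄ = 0.54.

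- One-sided: (1.159 + 0.573)² / 0.26² = 44.4, so 45. This matches.
- Two-sided: (1.381 + 0.573)² / 0.26² = 56.5, so 57.

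Other versions at two-sided 5% give 54 (unpooled), 57 (arcsine) and 64 (continuity-corrected). None gives 45.

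**Step 2: power at 50 per group for 41% v 67%.**

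- One-sided: (0.26 − 1.645 × 0.0997)/0.0962 = 0.998, power 84.1%.
- Two-sided: (0.26 − 1.960 × 0.0997)/0.0962 = 0.672, power 74.9%.

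**Step 3: replace 67% by 64%.** Now p̄ = 0.525 and the difference is 0.23.

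- One-sided: n = (1.162 + 0.578)² / 0.23² = 57.2, so 58. Power at 50: (0.23 − 1.645 × 0.0999)/0.0972 = 0.676, or 75.1%.
- Two-sided: n = (1.384 + 0.578)² / 0.23² = 72.8, so 73. Power at 50: (0.23 − 1.960 × 0.0999)/0.0972 = 0.352, or 63.8%.

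At 64% the unpooled, arcsine and exact-binomial versions give 76.5%, 75.1% and 73.6% one-sided, and 65.8%, 64.2% and 66.2% two-sided. All are below 80%.

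**Step 4: separate the two effects.**

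| Power at 50 per group, control 41% | One-sided 5% | Two-sided 5% |
|---|---|---|
| 67% | 84.1% | 74.9% |
| 64% | 75.1% | 63.8% |
| Rate needed for 80% power | about 66% | about 69% |

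Moving from 67% to 64% costs 9.0 points of power one-sided and 11.1 points two-sided. Moving from one-sided to two-sided costs 9.2 points at 67%, before the rate is touched.

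**Step 5: sensitivity to the other inputs.**

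- Size of the comparison group: with 50 intervention cases and 64%, one-sided power reaches 80% at 67 comparison callers. Two-sided power is 77.6% with 109 and reaches 80% only at 133.
- Control rate: 382/939 = 40.7%, which rounds to the 41% used but comes from callers with no substance misuse. The substance-misuse callers give 49/109 = 45.0%. At 45% v 64%, power at 50 per group is about 61% one-sided and 48% two-sided.

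**The case against.** The best defence is that a comparison is powered on a difference, not on one arm. The protocol plans for 67 − 41 = 26 points, while the smallest margin it cites is 64 − 30 = 34 points. In that sense the plan is cautious, and this stands. It does not rescue the wording, which attaches the label to the CRAFT outcome itself.

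Second, the comparison group may exceed 50. That also stands: a modest increase restores 80% power at 64% if the test is one-sided. But the sample-size statement is made for equal groups and does not invoke a larger comparison group.

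Third, this is a feasibility pilot. Trial procedures makes feasibility, family members' engagement and within-subject change the primary goal, and Considerations of alternative approaches puts proof of concept ahead of efficacy. That limits the importance of the point. It does not remove it, because the comparison is described as a key analysis and is given a formal power claim.

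A reader might infer three stronger things that the documents do not support:

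- That 64% is the lowest CRAFT rate in the four trials. It is the CRAFT arm of the trial with the smallest margin, and the lower of only two rates quoted.
- That the web-course pilot ("Preliminary analyses suggested that VA-CRAFT did not lead to greater engagement in VA mental health or SUD treatment") shows 67% to be unattainable. That pilot enrolled families of Veterans who screened positive for PTSD and gave no coaching. The protocol uses the result as its reason for adding telephone support, so it is not an estimate for Coaching-CRAFT.
- That the whole gap between 45 and 73 per group comes from three percentage points. Part of it comes from the undeclared sidedness.

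**Conclusion.** The point holds in limited form. The 67% is underived and above the 64% cited, so calling it conservative is unsupported for the intervention rate, though defensible for the difference. The 45 per group is correct arithmetic only for a one-sided 5% test that the protocol does not declare. On that convention 50 per group is adequate at 67% and falls about 5 points short of 80% power at 64%. On a two-sided 5% test it falls about 5 points short at 67% and about 16 points short at 64%.

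These figures assume alpha of 5%, exactly 50 comparison callers, independent samples as planned, and a true control rate of 41%. More comparison callers would raise the power; a control rate of 45% would lower it. This is a minor correction to a secondary comparison and does not call the feasibility aims or the enrolment target into question.

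**What to change.** In Intervention comparisons:

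1. Delete the word conservative, or show how 67% was obtained and say that the caution lies in the difference rather than in the rate.
2. Declare alpha and whether the test is one-sided or two-sided. If two-sided at 5%, replace 45 by 57 and remove the statement that 50 exceeds the need.
3. Reconcile the 41% control rate with the 49/109 (45%) for substance-misuse callers before finalising any power figure.
4. State the power of the planned sample at both 67% and 64% under the declared convention. If 41% is kept and the groups are 50 and 50, this is 84% and 75% one-sided, with about 66% needed for 80% power; or 75% and 64% two-sided, with about 69% needed.
5. If more than 50 comparison callers will be used, give the planned number and recompute.

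The cost is a few sentences and a lower stated power. Enrolment, design and analysis method stay as they are.
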